9.1.2 Description of Assessment Instruments

Acceptability and Feasibility. Intervention credibility and patient expectations for intervention

success at baseline will be measured with the Credibility Expectancy Questionnaire (CEO) [17]; this is administered after their initial class. The Client Satisfaction Questionnaire (CSQ-8) [18] will be used post-treatment to assess satisfaction with treatment. We will also use qualitative responses to a detailed post-treatment interview to gain participants' and parents' feedback about intervention components and research procedures. Finally, it is critical that the amount of yoga practice at home be measured as accurately as possible. Participants will complete a yoga home practice questionnaire on a weekly basis. This tool was designed to capture both brief "micro" practice (e.g., focusing on breathing for a few minutes) as well as more extended home practice (e.g., engaging in a 15-minute asana routine). The tool will yield three indices of home practice: frequency of extended home practice, minutes of extended home practice, and frequency of micro home practice.

Participant safety. After each home practice questionnaire (i.e., weekly during the intervention period), we will ask participants and parents whether participants experienced any injuries as a result of yoga. At the end of the study intervention (M3), we will administer the Systematic Assessment of Treatment-Emergent Events – General Inquiry (SAFTEE) [19]. This allows us to systematically assess number of adverse events, severity, and resulting impairment. To assess pregnancy, the adolescent will be asked in private whether there is a possibility of pregnancy. If they report that they may be pregnant, either at baseline or during follow-up, they will be excluded from study participation as our yoga protocol is not modified for pregnancy. Finally, any time a participant (or parent) reports an adverse event to any staff member, a research assistant will contact the participant or parent or both to ascertain information for recording of the adverse event. For adverse events ascertained by any of these three possible methods, the research assistant gets information on what happened, start and stop dates, severity, functional impact, interactions with healthcare professionals, perceived cause, and possible relation to study participation. For more information and details on coding of AEs, please see DSMP.

Note that the QIDS also serves as a safety assessment, as it allows staff to assess a) clinical deterioration and b) suicidality. The BDI also assesses suicide. Any suicidality or clinical deterioration triggers a risk assessment. An AE/SAE is recorded if the participant meets criteria for an AE/SAE (see DSMP)—i.e., makes an attempt to hurt themselves, does hurt themselves, or is hospitalized. Suicide ideation or clinical deterioration in and of themselves do not necessarily constitute an AE.

Assessment of depression. In order to characterize the sample, we will assess whether participants meet criteria for major depressive disorder using relevant modules of the Mini International Neuropsychiatric Interview for Children and Adolescents (MINI-KID [20]). We will also use the MINI to determine whether participants meet exclusionary criteria. Our primary outcome of depression severity (adolescent interview) will be assessed using the 16-item QIDS-A-CR [12, 13] which has been psychometrically validated for adolescents [14]. The Patient Health Questionnaire – 8 item (PHQ-8;[21]) does not include a suicide item) will be used in an interview format for screening purposes only, as it is simple to administer.

Assessment of secondary outcomes. Adolescents will complete the Beck Depression Inventory-II (BDI; [22], a self-report measure of depression symptom-severity. We will also assess impairment using the Columbia Impairment Scale (CIS; [23]), which is a 13-item, self- or parent-report, that measures four areas of functioning: interpersonal relations, broad psychopathological domains, functioning in job or schoolwork, and use of leisure time. Items are rated on a Likert scale ranging from 0 (no problem) to 4 (very big problem). Anxiety will be assessed by revised version of the Screen for Child Anxiety Related Emotional Disorders (SCARED-R; [24, 25]), a 41-item self-report questionnaire designed to measure symptoms and severity of anxiety disorders in children age 8 to 17. We will assess sleep using the 8-item PROMIS Sleep Disturbance questionnaire, which has been validated in adolescents [26].

Assessment of potential mechanisms of action. We will assess metacognitive awareness (decentering) with the Toronto Mindfulness Scale (TMS), which has a decentering subscale and a

curiosity subscale [27]. We will assess self-compassion with the 26-item Self-Compassion Scale (SCS)[28]. This scale can yield a general self-compassion score and has previously been used with adolescents [29].

Other assessments. Finally, we will use the International Physical Activity Questionnaire (IPAQ) [30], a self-report measure of physical activity. We have also adapted this scale to measure amount of yoga practice participants engaged in during the follow-up time period. We will assess antidepressant medication use with the interview-based Treatment Response to Antidepressant Questionnaire (TRAQ) [31]). We will use the Child and Adolescent Services Assessment (CASA)[32] interview to assess other mental health treatment. If a participant is engaged in psychotherapy but the participant and parent are unclear as to whether it is CBT, we will use the Psychotherapy Practice Scale-Patient Depression Care Version [33] to help determine whether it is likely that the participant is engaged in CBT. This questionnaire will be modified to include some open-ended questions about the nature of the participant's psychotherapy. We will use the Perceived Cohesion scale to assess group cohesion.

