4.2 Exclusion Criteria

Phase 1 (Focus Group) Exclusion Criteria – Adolescents

- a) Adolescents may not have current suicide ideation or behavior that warrants immediate treatment. They may have passive ideation (i.e., thoughts that life is not worth living), but

may not have active suicide ideation, intent, plan, or an attempt within the previous 6 months. We will not actively assess this for Phase 1, but we will exclude an adolescent if they indicate they have active suicide ideation.

- b) Adolescents cannot currently be engaged in yoga classes, as these are the study interventions.

Phase 2, Phase 3 Study A, and Phase 3 Study B Exclusion Criteria – Adolescents

Exclusion criteria for Phase 2, Phase 3 Study A, and Phase 3 Study B are identical.

- a) QIDS- A-SR may not be higher than a score of 21. This ensures that adolescents are not severely depressed.
- b) Adolescents may not meet criteria for the following:
 - i. Autism spectrum disorder (AS) “cannot be ruled out” (via MINI), and symptoms are of sufficient severity to interfere with study treatment per clinician judgment;
 - ii. Current psychotic disorder
 - iii. Lifetime history of a manic episode
 - iv. Anorexia or Bulimia in past 3 months
 - v. Substance use disorders in past 12 months, and symptoms are of sufficient severity to interfere with study treatment per clinician judgment

These will be assessed with the Mini-International Neuropsychiatric Interview (MINI).

- c) Adolescents may not have current untreated active suicide ideation or behavior. They may not have had a suicide attempt in the previous 6 months. They may not have suicide ideation that is so severe that the study clinician judges it will interfere with study participation (e.g., if the clinician judges they need a higher level of treatment now or potentially very soon). This means that adolescents with active suicide ideation may be included if they are receiving stable mental health services (e.g., therapy, counseling) and suicidal ideation is known to the mental health provider. Adolescents may be included if they have passive ideation (i.e., thoughts that life is not worth living) but are not in active treatment.
- d) Adolescents cannot currently be engaged in yoga classes, as this is the study intervention.
- e) Adolescents cannot be pregnant as yoga should be modified for pregnancy [15].

Parent Exclusion Criteria for all Phases

None. Please see parent inclusion criteria above.

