5.3 Concomitant Interventions

5.3.1 Allowed Interventions

Once a participant is enrolled in the study, participants will not be excluded for any concomitant intervention. For example, if a participant begins outside yoga classes while they are in the study, we will record that information, but not require that they discontinue study interventions. If a participant changes their dose of antidepressant medication, or outside therapy, we will record that information, but not require that they discontinue study participation.

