If it is not possible to conduct study follow-up assessments in person, they will be conducted by telephone and via REDCap survey (For self-report questionnaires).

Participants will have the option of being paid in one of three ways for assessments conducted by phone:

- a. We can hold the cash for them until a date when study staff may meet them in person to give them the cash.
- b. If participants have signed consent to allow emails, we can send them an electronic Amazon gift card
- c. We can send participants a check by mail.

Phase 2 and 3 Visits:

- Weekly for 12 weeks
 - Study classes/groups
 - Homework Questionnaire
 - Injuries due to yoga
 - CEQ;
 - Perceived Cohesion Scale (after initial class only)
 - Any other AEs reported to RAs
- Month 1
 - Pregnancy question
 - Any other AEs reported to RAs
 - QIDS
 - Yoga Practice (IPAQ format)
 - Payment: adolescent - \$20; parent - \$20
- Month 2
 - Pregnancy question
 - Any other AEs reported to RAs
 - QIDS
 - Yoga Practice (IPAQ format)
 - Payment: adolescent - \$20; parent - \$20

- Month 3 (Final evaluation for Phase 2)
 - CSQ-8
 - Qualitative interview
 - SAFTEE
 - Pregnancy question
 - Any other AEs reported to RAs
 - MINI – Mania/hypomania module and Suicidality module
 - QIDS
 - BDI
 - CIS
 - SCARED
 - TMS
 - SCS
 - PROMIS-Sleep
 - Yoga Practice (IPAQ format)
 - TRAQ
 - CASA
 - Perceived Cohesion Scale
 - Payment: adolescent - \$30; parent - \$30

Phase 3 Visits Only:

- Month 6
 - Homework questionnaire
 - Any other AEs reported to RAs
 - QIDS
 - BDI
 - CIS
 - SCARED
 - Yoga Practice (IPAQ format)
 - TRAQ
 - MINI – Mania/hypomania module and Suicidality module
 - CASA
 - Payment: adolescent - \$40; parent - \$40
 -
- Month 9 (Final evaluation for Phase 3)
 - Homework questionnaire
 - Any other AEs reported to RAs
 - QIDS
 - BDI
 - CIS
 - SCARED
 - Yoga Practice (IPAQ format)
 - TRAQ
 - MINI – Mania/hypomania module and Suicidality module
 - CASA
 - Payment: adolescent - \$50; parent - \$50

NOTE: M9 visit only included for participants who signed a consent form version dated 12/1/2020 or earlier.

6.2.5 Completion/Final Evaluation – Phases 2 and 3

Even if adolescents drop out of study treatment, we will attempt to collect data at all assessment

points if adolescents and parents agree to it.

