7.1 Specification of Safety Parameters

Safety issues will be minimal in Phase 1 given that participation involves only a single focus group, no yoga classes, and no formal assessment of suicidality. However, should an issue arise (e.g., a voluntary report of suicide ideation from one of the adolescent participants), staff would manage it in the same way that they would manage it in Phases 2 and 3.

Please see Table 3 for a summary of safety issues, how they are assessed, when they are assessed, and relevant staff actions.

Table 3. Assessment and Management of Safety Issues, Summary, Phases 2 and 3.

| Safety Issue | How assessed | When Assessed in Phase 2/Phase 3 | Relevant Research Staff Actions |
|------------------------|--|---|---|
| Suicidality | QIDS, BDI, MINI Participant/parent report to research staff | B1, M1, M2, M3, M6*, M9* B1, M3, M6*, M9* Any point | Immediate clinical assessment as described in DSMP |
| Clinical deterioration | Change in QIDS score | M1, M2, M3, M6*, M9* | Immediate clinical assessment as described in DSMP |
| Injuries due to yoga | Structured self-report | Weekly during first 3 months | Follow until resolution; may result in changes to yoga instructor manual |
| Pregnancy | Single interview question | BL1 (exclusion) M1, M2 | Discontinuation from intervention |
| Other AEs | SAFTEE CASA Participant/parent report to research staff | M3 BL1, M3, M6*, M9* Any point | If related to study participation, follow resolution; potential changes to procedures particularly if AE is also unexpected |

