8. INTERVENTION DISCONTINUATION

Adolescents will be discontinued from an intervention in the following circumstances:

- If a parent, the adolescent, their primary care provider, or their mental health provider does not believe it is in the best interest of the adolescent to continue. As soon as an MPI is informed of this, she will speak with the participant about discontinuation. There may be circumstances (e.g., worsening depression, an injury in yoga class) when the MPI reaches out to a primary care provider, MH provider, or parent to actively inquire if they have concerns about the adolescent continuing to participate.
- If a parent or adolescent choose to discontinue the adolescent's attendance.
- If one of the MPIs, in consultation with the relevant instructor or therapist, finds the adolescent to be so disruptive to the rest of the class that they have a repeated and substantive negative impact on the other participants.
- If the adolescent does not or is unable to follow guidelines regarding being in a private space when participating in the video-based intervention.

Participants will continue with subsequent assessments with their (parent and adolescent) permission. Assessment schedule and assessments used will not change.

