9.5 Outcomes

9.5.1 Primary Outcome

There is no single primary outcome, as this is a treatment development study.

We monitor treatment development outcomes (correspondingly described in Table 5) throughout Phases 2 and 3. Target outcomes were chosen on face validity, clinical experience, and, when available, relevant clinical literature. After the pilot open trial (Phase 2), and at 2 time points throughout the Phase 3 pilot RCT (i.e., after enrolling 17 patients and 34 patients), the scientific team will convene to discuss how our actual procedural outcomes compare to the target outcomes. Discrepancies will result in: 1) investigation (using qualitative or other data) of the reason for the failure to meet this outcome; and 2) discussion amongst the research team. Depending on the nature of the discrepancy, we may modify recruitment procedures, assessment procedures, instructions to participants, instructor training procedures, or other aspects of the trial. In addition, Drs. [name] and [name] and the lead yoga instructor will review any adverse events that are possibly, probably, or definitely related to the study intervention to determine whether any changes need to be immediately made to the yoga instructor manual to prevent such events from occurring in the future.

Primary data analyses will be focused on feasibility and acceptability (see Table 5) using intent-to-treat population. Study measures and endpoints will continue to be collected for all enrolled participants, even in the event of premature discontinuation of the study intervention. To mitigate the problem of missing data, our RAs will try to reach participants to encourage them to schedule/complete the assessment via multiple methods that a participant (and their parent) have said are acceptable, including texting, voicemail, or email.

Table 5. Target Outcomes – Phase 2 and 3.

| Description (Assessment method) | Target |
|--|--|
| Feasibility and Acceptability-- Hatha yoga, CBT | |
| Acceptability (qualitative interview) | Most feedback positive; few substantive negative comments. Negative comments used to enhance procedures. Comments regarding video-based vs.in-person classes used to guide decisions about modality for future research. |
| Credibility at baseline (CEQ) | Average > 15 (i.e., midpoint score between low and high credibility) on each of 3 items |
| Expectancy at baseline (CEQ) | Average > 15 (i.e., midpoint score) on each of 3 items |

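### Section 9.1.2 removes a participant who may be pregnant during follow-up from the study, while Table 3 only stops the intervention

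*Combined protocol and SAP*

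**What the plan says.** Section 9.1.2 (Participant safety) describes the private pregnancy question and then sets the consequence of a report of possible pregnancy: "either at baseline or during follow-up, they will be excluded from study participation as our yoga protocol is not modified for pregnancy". Baseline and follow-up are treated alike.

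The pregnancy row of Table 3 (Section 7.1) gives timing and staff action as "BL1 (exclusion) M1, M2 | Discontinuation from intervention". Exclusion is attached to Baseline 1.

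Three other places say what happens once an intervention stops:

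- Section 8: "Participants will continue with subsequent assessments with their (parent and adolescent) permission. Assessment schedule and assessments used will not change".
- Section 9.5.1: "Study measures and endpoints will continue to be collected for all enrolled participants, even in the event of premature discontinuation of the study intervention".
- Section 6.2.5 opens: "Even if adolescents drop out of study treatment, we will attempt to collect data at all assessment", and makes this subject to the family's agreement.

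Section 9.3 specifies intent to treat with all available data. Pregnancy is an eligibility matter in Section 4.2(e): "Adolescents cannot be pregnant as yoga should be modified for pregnancy". Section 8 lists the circumstances for stopping an intervention, and pregnancy is not among them.

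**The concern.** Being excluded from the study and stopping the classes are different events, and most of this protocol treats them differently. An adolescent who stops classes is still followed. On its plain words, an adolescent who is excluded from participation is not. The same report therefore has two prescribed consequences, depending on the section that staff consult.

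Two things could be lost. The first is monitoring. The participants are depressed adolescents, and Section 9.1.2 notes that "the QIDS also serves as a safety assessment", covering both deterioration and suicidality. Ending assessments would end that check for reasons unrelated to mood. The second is data. Missed visits would probably count against the Table 5 retention targets, which belong to the feasibility aim that Table 4 marks as primary. The M3 QIDS change would also be missing for that participant, and Section 9.5.2 names it as the primary outcome of the later efficacy study.

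**Working it through.** The plan gives no figure to reproduce here. The check is a comparison of text, followed by a count of what the literal reading would remove.

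**1. The rules side by side**

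| Time of report | Section 9.1.2 | Table 3 |
|---|---|---|
| Baseline 1 | excluded from participation | exclusion |
| M1, M2 | excluded from participation | stop the intervention |
| M3 | excluded from participation | time point not listed |

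The two agree at baseline and differ after enrolment. The M3 row arises because Table 2 and Section 6.2.4 ask the pregnancy question at M1, M2 and M3, whereas Table 3 lists only M1 and M2 after baseline.

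**2. Does another section settle it?** Sections 6.2.5, 8 and 9.5.1 all continue assessment after the intervention stops, so Table 3 read with 9.5.1 points to continued follow-up. But no section says that the 9.1.2 wording means only the classes, and Section 8 does not name pregnancy. The conflict is not expressly resolved.

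**3. What does participation mean in this protocol?** Usage varies. Section 5.3.1 has two parallel sentences. For outside yoga, the participant need not stop study interventions. For a change in medication dose or outside therapy, staff will record it "but not require that they discontinue study participation". That is loose usage. Elsewhere the term is wider than classes: Section 7.3 records events up to the last day of study participation, and Section 4.3 refers to compensation for study participation, which Table 2 pays by assessment visit.

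**4. Assessments lost on the literal reading** (Table 2, Phase 3, assuming the reporting visit is itself completed)

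| Report at | QIDS visits lost | Also lost |
|---|---|---|
| M1 | M2, M3, M6, any M9 | M3 SAFTEE; MINI suicidality at M3, M6, any M9 |
| M2 | M3, M6, any M9 | M3 SAFTEE; MINI suicidality at M3, M6, any M9 |
| M3 | M6, any M9 | MINI suicidality at M6, any M9 |

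M9 applies only to participants who signed a consent version dated 12/1/2020 or earlier. In Phase 2 the last visit is M3.

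**5. Scale against the M3 retention target** (80%, Table 5; assumes full planned enrolment, with everyone enrolled in the denominator)

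- Study A: 0.80 × 34 = 27.2, so 28 must complete M3 and 34 − 28 = 6 may be missed. One participant is 1/34 = 2.9%.
- Phase 2: 0.80 × 12 = 9.6, so 10 must complete and 12 − 10 = 2 may be missed.

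One participant lost before M3 would use 1 of the 6, or 1 of the 2.

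**The case against.** The best defence is that the intended reading is clear. Table 3 is the operational table of staff actions, and Section 9.5.1 continues data collection for everyone enrolled. Section 9.1.2 mainly describes instruments, and the reason it gives concerns yoga, which has no bearing on interviews or questionnaires. Section 5.3.1 shows that the authors use the terms loosely. Harm would require staff to follow an instrument description over the safety table, and nothing suggests they would. This is fair, and it is why the consequences here are conditional on a literal reading. It does not remove the conflict, because 9.1.2 states an operative rule for enrolled participants and no other text corrects it.

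The objections to the scale figures also have weight. No pregnancy rate is given, and enrolment is open regardless of gender, so not all 34 need be at risk. Table 5 is also read for the whole enrolled group and for subgroups, so 34 is not the only denominator. A missed target leads to investigation and discussion, not to failure of the trial. Phase 2 is probably complete: Section 7 reports 19 yoga enrolments by 3/13/2020, against 12 planned for Phase 2. That is an inference, since the documents give no phase dates. The figures show scale only and do not predict loss.

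The M3 omission in Table 3 may be deliberate, since the intervention ends at M3 and little is left to stop. For the same reason, exclusion at M3 under 9.1.2 would act almost entirely on follow-up assessments.

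**Conclusion.** The inconsistency is real, but minor. At baseline the sections agree. After enrolment, Section 9.1.2 prescribes leaving the study where Table 3 prescribes stopping the intervention, and no section expressly reconciles them. The likely intent is the Table 3 rule.

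Confidence is high that the texts differ. The consequences depend on staff following 9.1.2 literally and on a pregnancy report occurring after enrolment, for which the documents give no rate. Cases are probably few. Each would cost one participant's remaining outcome and safety assessments, and at most 1 of the 6 missed M3 visits that the Study A target allows. Sample size and analysis are unaffected.

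**What to change.** In Section 9.1.2, limit exclusion from participation to baseline. For a report after enrolment, state that the study intervention is discontinued and that all scheduled assessments continue with the permission of parent and adolescent. Add pregnancy to the list in Section 8, so that its rule on continued assessment plainly applies.

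Two smaller clarifications can go in at the same time. State whether discontinuation applies to both arms: the reason given is specific to yoga, but neither 9.1.2 nor Table 3 is limited to the yoga arm. Align the M3 pregnancy question between Table 2 and Section 6.2.4 on one side and Table 3 on the other.

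The cost is protocol wording only: one sentence in 9.1.2, one bullet in Section 8 and one cell in Table 3. Because the pilot's procedures are meant to prepare a fully powered trial, the correction would carry forward.

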Participants may also show significant clinical deterioration, as defined as a QIDS total score of 16 or greater and an increase in QIDS score of 6 or greater from the previous QIDS assessment. This will also trigger a clinical evaluation and a determination of the best course of action for the adolescent based on clinical judgment. Typically, this will include notification of a parent and outpatient mental health provider (if the participant has one) or offer of referrals to an outpatient provider. Actions could also include facilitation of higher levels of care (e.g., inpatient hospitalization).

A participant who has undergone a suicide risk assessment or who has had clinical deterioration may continue to participate in the study unless the study PIs, in concert with the participant's parent and healthcare providers, deem study participation to increase risk for this particular participant. Participants who are hospitalized due to concerns about suicidality may be discontinued from the study if parents/

clinicians/ MPIs determine it to be in the best interest of the participant. However, they may also continue if that is determined to be in the best interest of the participant.

Additional Protections for Vulnerable Subjects

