7.3 Adverse Events and Serious Adverse Events

Adverse Event (AE) definition: An adverse event (AE) is any unfavorable and unintended diagnosis, symptom, sign (including an abnormal laboratory finding), syndrome or disease which either occurs during the study, having been absent at baseline, or if present at baseline, appears to worsen. Adverse events are to be recorded regardless of their relationship to the study intervention.

Serious Adverse Event (SAE) definition: A serious adverse event (SAE) is one that meets one or more of the following criteria:

- Results in death
- Is life-threatening (places the subject at immediate risk of death from the event as it occurred; includes a suicide attempt or drug overdose)
- Results in inpatient hospitalization or prolongation of existing hospitalization
- Results in a persistent or significant disability or incapacity
- Results in a congenital anomaly or birth defect

An important medical event that may not result in death, be life threatening, or require hospitalization may be considered an SAE when, based upon appropriate medical judgment, the event

may jeopardize the subject and may require medical or surgical intervention to prevent one of the outcomes listed in this definition.

Study staff will record all reportable events with start dates occurring any time after informed consent is obtained at least until the final day of study participation. Each time participants attend yoga classes, we will inquire about injuries due to yoga. For all participants in either the open trial or pilot RCT, at Month 3 (end of intervention), study staff will administer the SAFTEE in order to inquire about the occurrence of AE/SAEs during the previous 3 months. This allows us to systematically assess number of adverse events, severity, and resulting impairment. Finally, any time a participant (or parent) reports an adverse event to any staff member, a research assistant will contact the participant or parent or both to ascertain information for recording of the adverse event. For adverse events ascertained by any of these three possible methods, the research assistant gets information on what happened, start and stop dates, severity, functional impact, interactions with healthcare professionals, perceived cause, and possible relation to study participation.

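### New or worsened suicidal ideation and depressive worsening meet the AE definition in Section 7.3, but Section 9.1.2 lets them go unrecorded as AEs

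*Combined protocol and SAP*

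**What the plan says.** Section 7.3 defines an AE as "any unfavorable and unintended diagnosis, symptom, sign" or similar finding that arises during the study, "having been absent at baseline, or if present at baseline, appears to worsen". It adds: "Adverse events are to be recorded regardless of their relationship to the study intervention".

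Section 9.1.2 (Description of Assessment Instruments) explains that the QIDS and BDI double as safety measures and that a positive finding prompts a risk assessment. It then spells out when an AE or SAE is recorded: the participant "makes an attempt to hurt themselves, does hurt themselves, or is hospitalized". It refers to the DSMP for the criteria and continues: "Suicide ideation or clinical deterioration in and of themselves do not necessarily constitute an AE".

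Section 7 treats a QIDS item 12 score of 1 or more as significant suicide risk. It defines significant clinical deterioration as "a QIDS total score of 16 or greater and an increase in QIDS score of 6 or greater from the previous QIDS assessment".

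Table 4 marks the Phase 3 aim that includes safety of both arms as primary. The Table 5 safety row names the SAFTEE and yoga injuries as its sources, and its target is that no related serious event or injury occurs. Section 7.4 provides for an annual AE summary to NCCIH and the Safety Monitoring Committee.

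**The concern.** The same event can be an AE under one section and not under the other. A teenager with no ideation at baseline who reports it at Month 2 has a new unfavourable symptom, which 7.3 says to record. Under 9.1.2 it need not be recorded without an attempt, self-harm or hospitalization.

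This matters because worsening depression and new ideation are harms that can arise in either arm. Section 7 anticipates suicidal ideation in some participants and lists ineffective intervention among the risks. The weekly structured safety question concerns yoga injuries only, and no AEs are expected with CBT. Without these events, the safety description in an aim marked primary is incomplete for both arms.

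**Working it through.** The plan states no figure on this point, so there is none to reproduce. The check applies the two sections to example cases, using the QIDS thresholds in Section 7. The scores are illustrative.

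| Case | Arithmetic | Section 7 flag | AE under 7.3? | Under 9.1.2 |
|---|---|---|---|---|
| A. Item 12: 0 at baseline, 1 at M2 | 1 − 0 = +1 | Suicide risk | Yes, new | Need not count |
| B. Item 12: 1 at baseline, 1 at M2 | 1 − 1 = 0 | Suicide risk | No, unchanged | Need not count |
| C. QIDS total: 10 at baseline, 16 at M1 | 16 ≥ 16; 16 − 10 = 6 | Deterioration | Yes, worse than baseline | Need not count |
| D. QIDS total: 20, 12, 18 (baseline, M1, M2) | 18 ≥ 16; 18 − 12 = 6; 18 − 20 = −2 | Deterioration at M2 | Not on the baseline test | Need not count |
| E. QIDS total: 10, 15, 20 (baseline, M1, M2) | steps of 5 and 5; 20 − 10 = 10 | None | Yes, worse than baseline | Not addressed |
| F. Suicide attempt or hospitalization | – | – | Yes, serious | Recorded |

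Cases B, D and F are consistent between the sections. B can occur because Section 4.2 allows passive ideation at entry, and active ideation if it is under stable treatment. The sections diverge in A and C. Case E shows that the deterioration flag compares with the previous QIDS while 7.3 compares with baseline, so neither can stand in for the other.

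The next question is whether cases A and C reach the AE record by another route. Section 7.3 lists three: the yoga-injury question, the SAFTEE at Month 3, and reports by a participant or parent. Table 3 adds the CASA, a service-use interview, for other AEs. Findings on the QIDS, BDI or MINI are not listed as a route, although Table 3 relies on them to detect suicidality and on the QIDS to detect deterioration. The SAFTEE is given only at Month 3, so ideation or worsening that begins later has no systematic symptom inquiry feeding the AE record.

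The last question is whether the events are counted elsewhere. Section 9.6 plans descriptive statistics and within-group change by arm, so mean QIDS change is reported. A mean can improve while individuals worsen. Section 9.5.2 does not list item 12 as an outcome, and no section specifies a count by arm of participants with ideation or deterioration.

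On scale, the documents give no rate for either event, so an expected number cannot be derived. What can be stated is the weight of one participant. If the 34 Study A participants split equally (an assumption), each arm has 34 / 2 = 17, and one unrecorded case is 1 / 17 = 5.9% of that arm.

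**The case against.** The strongest reply is that the disputed sentence in 9.1.2 is discretionary and partly right under 7.3. Ideation unchanged from baseline (case B) and a rebound that stays below the baseline score (case D) are flagged by the risk procedures without being worse than baseline. That stands, and it rules out reading 9.1.2 as a blanket exclusion or treating every QIDS-defined deterioration as an AE. It does not cover cases A and C, for which the list in 9.1.2 is narrower than 7.3.

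A second reply is that the DSMP, which 9.1.2 cites for AE criteria and coding, may contain the missing rule. That is possible. The DSMP is not part of this document, and the two sections conflict as written.

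A third is that nothing is hidden. Each event triggers a clinical evaluation, suicide assessments are documented in writing, and some events may enter through the SAFTEE, the CASA or a participant's report. This also stands. A reader might infer that these harms go undetected or unmanaged, and the documents do not support that. The gap is in AE recording and tabulation.

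Two other stronger readings also fail. One is that the Table 5 safety target could be met falsely. That target concerns related serious events and injuries, so adding non-serious AEs would leave it unchanged. The other is that counts would vary from coder to coder. In Phase 3, Section 7.4 gives the coding of severity, causality and expectedness to the non-blind investigator alone. The weakness is that this document gives that person no stated criterion.

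**Conclusion.** The concern holds in limited form. Sections 7.3 and 9.1.2 give different answers for ideation that is new or worse than baseline, and for QIDS-defined deterioration that is also worse than baseline. Such events can be left out of the AE tabulation, the Table 5 safety row and the annual summary to the monitors.

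The number of participants affected cannot be stated, because no rate is given. A reader might infer that a large share of the safety signal is lost, but nothing in the documents allows that to be estimated. The conclusion assumes that worsening in 7.3 is judged against baseline, and that the DSMP does not already settle the matter. This is an inexpensive correction that would make the safety part of a primary aim more complete. It is not a flaw in detection or in clinical response.

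**What to change.** Reconcile Sections 7.3 and 9.1.2, and the DSMP they rely on, so that ideation or depressive worsening that is new or worse than baseline is recorded as 7.3 requires. State the comparison point explicitly, since the deterioration definition uses the previous QIDS and 7.3 uses baseline. This concerns recording only; the triggers for clinical evaluation need not change.

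Whichever AE label is kept, add a descriptive line to the Table 5 safety row giving, by arm:

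- the number of participants with new or worsened ideation relative to baseline on QIDS item 12;
- the number who at any visit meet the plan's QIDS deterioration definition.

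The QIDS is already scheduled at baseline, Months 1, 2, 3 and 6, and at Month 9 for earlier consents, so no new assessment is needed. The counts should come from the QIDS data rather than from evaluation notes, because Section 7 promises a written record only for suicide assessments. The cost is a wording change in the protocol and DSMP, one table line, and a longer safety listing that looks slightly less favourable.
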